any participants refuse or are unable to complete the questionnaires on the computer, they will be permitted to use hard-copy paper versions of the questionnaires. Participants will also be provided the option to complete questionnaires over the phone. The CRC will contact participants (in person or via telephone) daily for two days to remind them to complete and return the surveys. If study participants fail to complete the surveys within seven days of the expected time point, we will report the data as missing and document the reason for incompleteness. Table 4 details the schedule for administering the self-report measures. At enrollment all participants will be mailed the *Actigraph GT3X+* (together with instructions (Appendix V) on how to use the *Actigraph*) for 7 days of wear; minimum acceptable use is 4+ days with 10+ hours of recorded data around day 85-95 post-transplant and prior to the intervention initiation around day 100 post-transplant. After baseline physical activity data collection, participants will mail back the *Actigraph* in prepaid envelopes we will provide. In addition to the *Actigraph*, participants will also be mailed the MEMS Cap (together with the instructions (Appendix W) on how to use the MEMS Cap) for medication (immunosuppressant) adherence assessment over the entire duration of the intervention starting at the time of baseline surveys around day 85-95 post-transplant. All participants will complete baseline assessments approximately 85-95 day post-transplant. All participants will then complete follow-up assessments at Week-9 (with a 1 week window) and at Week-18 (+/- 1 week window) of intervention initiation.

Table 4: Administration of Self-Report Measures

Participant	Baseline	Week-9 (+ 1 week window)	Week-18 (+/- 1 week window)
Patient Measures:			
Demographics	X		
FACT-BMT	X	X	X
PROMIS-Fatigue 8a	X	X	X
PROMIS-PF-20	X	X	X
HADS	X	X	X
PCL (PTSD)	X	X	X
LOT-R	X	X	X
PANAS	X	X	X
GQ-6	X	X	X
SWLS	X	X	X
Flourishing Scale	X	X	X
Brief Cope	X	X	X
MARS-5	X	X	X
SSEQ	X	X	X
Accelerometer	X	X	
MEMS-Cap		Longitudinal from baseline through week 9	

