Weekly phone sessions for positive psychology intervention: Participants in the intervention group will be asked to complete the 9 weekly PP exercises and to speak with the interventionist weekly. Weekly phone sessions will last approximately 15-20 minutes. Prior to completing each phone session, participants will be asked to rate their current level of happiness and optimism, using a 10-point Likert scale. Immediately after completing the exercise and phone session, participants will rate the ease of exercise/session completion, overall utility of the exercise/phone session, and their current levels of happiness and optimism, all using 10-point Likert scales. These calls will be recorded using the SONY IC Recorder ICD-PX370 so that a percentage (10%) of these recordings can be reviewed by [name], to ensure that the PP intervention is being delivered as described in the protocol. Given the results of our prior PP studies in medical populations yielding a 64-85% completion rate of the exercises, our recent proof-of-concept trial (18-225) yielding 100% completion rate in this population, and given that this is a feasibility study (i.e., we want to assess participants' willingness to complete the phone sessions), we will expect participants to complete at least 6 PP exercises. In other words, if a participant completes at least 6 sessions, missed sessions will not be considered a deviation from the protocol.

All participants will receive a \$50 check after completion of the intervention. Participants in the usual care group will also receive a \$50 at the same timepoint. All participants (in either the usual care group or intervention group) who complete 18-week follow-up assessments will receive an additional \$50 check.

PROTOCOL TITLE: Randomized Trial of a Positive Psychology Intervention for Patients with Hematologic Malignancies Undergoing Hematopoietic Stem Cell Transplantation

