Follow-up assessments: During Week 8 of the intervention, all participants (those in the intervention group and the usual care group) will be mailed (or given in-person during a routine follow-up clinic visit) an accelerometer to wear for 7 days in order to assess physical activity at follow-up. Then, at Week 9, participants will return the accelerometer and MEMS Cap, and will repeat self-assessment questionnaires obtained at the beginning of the study either in-person during a routine follow-up clinic visit, over the phone, or via a REDCap survey link e-mailed to them, depending on participant's preference. Furthermore, participants in the intervention group will be asked to provide feedback about the program via a recorded exit interview over the phone.

Positive Psychology Program Content: All phone sessions will include (a) a review of the ease and utility of the week's PP exercise, (b) a discussion of the rationale of the next week's PP exercise through a guided review of the PP manual, and (c) assignment of the next week's PP exercise. During the calls, the interventionist and participant will also review the next section of the treatment manual and prepare for the upcoming week's exercise.

9.8 *Procedures performed to lesson the probability or magnitude of risks*

We will ensure that contact with participants is confidential by using only the phone numbers and other contact information that are specifically allowed by the participants. We will not leave study-related messages for participants unless expressly allowed by participants. Upon enrollment, we will ask all participants for the preferred times for calls and if it is acceptable to leave voice messages on their phones. We will adhere to any and all patient requests regarding contact.

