- **Disease Worsening/Mortality:** Given the burden of treatment for patients with hematologic malignancies undergoing HSCT, we do anticipate that a minority of participants will be unable to complete the study protocol due to deteriorating health or death. Our research team has given considerable thought to this concern and adequately powered the study to account for missing data. Based on prior work, we anticipate a 15% attrition rate. The study CRCs will maintain detailed records for patient attrition due to disease-related factors.
- **Refusal to Participate:** Participants who are successfully recruited into the study but later refuse to participate in subsequent intervention sessions pose a threat to the proposed study. In our previous trial, our refusal to participate rate after study enrollment was quite low and all participants who started the intervention actually completed the all the intervention sessions. Again, the CRCs will maintain detailed records for patient refusals.
- **Loss of Contact:** Another source of attrition involves those subjects who are successfully recruited into the study but who cannot be located for subsequent follow-up assessments. Like attrition due to subject refusal, attrition due to loss of contact poses a threat to the proposed study. We do not anticipate this to be a major

PROTOCOL TITLE: Randomized Trial of a Positive Psychology Intervention for Patients with Hematologic Malignancies Undergoing Hematopoietic Stem Cell Transplantation

issue for the proposed study given the intensive and frequent outpatient follow-up visits for patients with hematologic malignancies during the first six months post-HSCT.

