- Participant Adherence: To minimize attrition, we plan to use multiple strategies to reduce drop-out. Potential participants will be invited to participate in the baseline assessment during which time participants will receive a thorough explanation of the study treatments, requirements, and follow-up procedures. Study staff will emphasize the patient's responsibility as a research participant, reiterate confidentiality, and work to develop good rapport. We will make a concerted and systematic effort to facilitate adherence to the completion of follow-up assessments. This task will be accomplished by: (1) obtaining longitudinal participant-reported measures during regular follow-up appointments; (2) providing participants with remote access to complete the longitudinal study measures; and (3) making reminder phone calls and administering the study measures over the phone if necessary for participants who do not have appointments in the window for assessment completion.

Data Safety and Monitoring Plan

The following procedures will be followed, in compliance with NIH requirements, to ensure the safety of study participants and the validity and integrity of data.

- Range of Safety Reporting: [name] will review all data pertaining to safety during the weekly research team meeting. These include adverse events (AEs) and serious adverse events (SAEs), but also other data that may reflect differences in safety such as treatment retention rates and reasons for dropout.

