PROTOCOL TITLE: Randomized Trial of a Positive Psychology Intervention for Patients with Hematologic Malignancies Undergoing Hematopoietic Stem Cell Transplantation

will be reviewed and a determination made of whether there was any possible relevance to the study interventions. Additional reporting to the NIH will be made according to their respective regulations governing SAE reporting.

- **Non-Serious Adverse Events:** The research team will review monthly summary reports of the numbers and rates of adverse events by treatment group. These reports will include types of events, severity, and treatment phase.
- **Other Safety-Related Reports:** The research team will review weekly summary reports of treatment retention and reasons for dropout, by treatment group.

Monitoring of Data Quality by the research team:

The research team will review the following items on weekly basis to ensure data quality and completeness:

- Total enrollment compared with anticipated enrollment
- Number of ineligible patients registered
- Proportion of missing participant-reported outcomes
- Proportion of other missing data
- Number of participants lost to follow-up
- Number of participants completing the study

Additionally, the research team will receive a report on safety and outcome data for the trial:

- Number of deaths, listed by cause
- Number and types of SAEs
- Number and types of reportable AEs
- Number of participants with primary outcomes
- Number of participants with secondary outcomes

ClinicalTrials.gov Requirements

As per Public Law 110-85, this is an applicable clinical trial and will be registered and results will be reported with ClinicalTrials.gov. The CRC will be responsible for handling ClinicalTrials.gov requirement for this project under [name] (PI) oversight. She will work closely with the Partners Human Research Affairs QI Program to register the trial prior to enrolling the first subject. Once a record is established, she will confirm accuracy of record content; resolve problems; and maintain records including content update and modification. She will also be responsible for aggregate results reporting and AE reporting at the conclusion of the project. We will ensure that summary results will be reported to clinicaltrials.gov no later than one year after the primary completion date.

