13.0 Risks to Subjects*

The risks to participating in this study should be relatively limited and is no more than minimal risk. Given this is a supportive oncology study, we do not anticipate any study-related events meeting the FDA definition of a SAE (i.e., any fatal event, immediately life-threatening event, permanently or substantially disabling event, event requiring or prolonging inpatient hospitalization, or any congenital anomaly). This study population is comprised of individuals undergoing HSCT who frequently experience disease worsening, high rate of symptoms, and hospitalizations from the underlying disease and/or side effects of treatment. Therefore, regular fluctuations in cancer-related symptoms, disease worsening, hospitalizations, emergency department visits, and deaths are to be expected throughout the study, and we will not consider or report such events as SAEs in this trial.

We anticipate no physical risks to participating in this study. Study participants may experience discomfort from discussing psychological experiences and could experience the evaluation as intrusive. Study participants who do not find any benefit from participation may find this upsetting. Activities to obtain data through the baseline and follow-up assessment battery may provide some inconvenience to study participants.

Non-Serious Adverse Events: The IRB will be provided with unblinded summaries of study related non-serious adverse events by treatment group at the continuing reviews. These reports will include types of events, severity, and treatment phase. To date, we have had very few non-serious events in our supportive care studies.

As this is a behavioral study, there are no ingested medications, and no biomedical procedures. It is unlikely that participants will be at any risk for physical harm as a result of study participation.

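### Adverse-event rates are reported by arm, but in Weeks 0-9 only PATH has weekly study calls and no common way of finding events is stated, so PATH will tend to show more events at equal true rates

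*Combined protocol and SAP*

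**What the plan says.** **Reporting by arm (protocol Section 11.0).** On non-serious adverse events: "The research team will review monthly summary reports of the numbers and rates of adverse events by treatment group". On retention: "The research team will review weekly summary reports of treatment retention and reasons for dropout, by treatment group". The same section includes, among the data reviewed for safety, "other data that may reflect differences in safety such as treatment retention rates and reasons for dropout". Section 13.0 adds a report to the ethics board: "The IRB will be provided with unblinded summaries of study related non-serious adverse events by treatment group at the continuing reviews". Both adverse-event reports are to be broken down by treatment phase.

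**Contact in PATH (Section 9.7).** "Participants in the intervention group will be asked to complete the 9 weekly PP exercises and to speak with the interventionist weekly".

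**Contact in both arms.** Section 9.6: "All participants will then complete follow-up assessments at Week-9 (with a 1 week window) and at Week-18 (+/- 1 week window) of intervention initiation". Section 9.7 adds the accelerometer hand-over: "During Week 8 of the intervention, all participants (those in the intervention group and the usual care group) will be mailed". Table 4 lists the measures at baseline, Week 9 and Week 18; none is an adverse-event item.

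**Other routes by which events could come to light.** Section 9.3 tracks social-work and mental-health visits in both groups. Section 9.5 takes GVHD and relapse from the health record. Section 11.0 refers to "intensive and frequent outpatient follow-up visits for patients with hematologic malignancies during the first six months post-HSCT". Section 12.0 lets any participant withdraw at any time, and they will be asked the reason. Section 13.0 asks participants to phone staff about device problems.

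**Status of safety.** Section 8.0 names no primary or secondary safety endpoint. Section 11.0 refers to Appendix X for the detailed monitoring plan; that appendix is not in the supplied text.

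**The concern.** A between-arm rate can be read as a treatment effect only if events are looked for in the same way in both arms. Here one arm has nine weekly conversations in which a participant can mention distress, upset or a wish to stop. The other has one device hand-over and one survey in the same period. A mild event in Week 2 can be voiced within days in PATH. In usual care it must be volunteered, be charted, or be remembered at Week 9, when no listed measure asks about it.

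At stake is how the by-arm adverse-event tables are read. PATH could look worse because it is watched more closely, and a real excess in usual care could be hidden. The feasibility, acceptability and efficacy analyses do not use these tables.

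**Working it through.** The plan states no adverse-event rate or detection rate, so there is no figure on this point to reproduce. The one related figure is the 15% attrition allowance in Section 10.2: 35 × 0.85 = 29.75, which agrees with the target of about 30 PATH completers from 35.

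**Adverse events, Weeks 0-9, equal true rates**

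From the documents: weekly calls in PATH (contact interval G = 1 week); first common assessment at Week 9 (G = 9 weeks in usual care). Assumed: events fall uniformly over Weeks 0-9, and an event is reported at the next contact with probability exp(−k × gap), where k = ln 2 / h and h is a recall half-life in weeks.

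Mean detection for interval G is f(G) = (1 − exp(−kG)) / (kG), and the apparent ratio is f(1)/f(9).

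For h = 4: k = 0.1733; f(1) = (1 − 0.8409)/0.1733 = 0.918; f(9) = (1 − 0.2102)/1.5596 = 0.506; ratio 1.81. In the same way:

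| h (weeks) | PATH f(1) | Usual care f(9) | Ratio, Weeks 0-9 | Ratio, Weeks 0-18 |
|---|---|---|---|---|
| 2 | 84.5% | 30.6% | 2.76 | 1.88 |
| 4 | 91.8% | 50.6% | 1.81 | 1.41 |
| 8 | 95.8% | 69.4% | 1.38 | 1.19 |
| 26 | 98.7% | 88.9% | 1.11 | 1.05 |
| complete recall | 100% | 100% | 1.00 | 1.00 |

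The Weeks 0-18 column is (f(1) + f(9)) / (2 × f(9)), because both arms share one schedule after Week 9.

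*If the Week-8 hand-over also brings out events.* Usual-care detection becomes (8 × f(8) + f(1))/9. For h = 2, f(8) = 0.338, so detection is (8 × 0.338 + 0.845)/9 = 0.394 and the ratio is 2.14. For h = 4, 8 and 26 it is 1.58, 1.28 and 1.08.

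*If a share s of events is charted in both arms.* The ratio is (s + (1 − s)f(1)) / (s + (1 − s)f(9)). With s = 0.5 and h = 2: (0.5 + 0.5 × 0.845)/(0.5 + 0.5 × 0.306) = 1.41; for h = 4 and 8 it is 1.27 and 1.16. With s = 1 it is 1.00.

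**Dropout**

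From the documents: 35 per arm, 15% attrition. Assumed: all of it occurs by Week 9 at a constant hazard, λ = −ln(0.85)/9 = 0.01806 per week, equal in both arms. PATH dropout is known at the next call. Usual-care dropout is known, at the latest, when the one-week window after Week 9 closes.

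- Week 4: 35 × (1 − exp(−4λ)) = 2.4 known in PATH, as few as 0 in usual care.
- Week 8: 35 × (1 − exp(−8λ)) = 4.7 against as few as 0.
- From Week 10: 35 × 0.15 = 5.25 in each arm.

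The zeros mark the largest possible gap, since usual-care participants can withdraw unprompted or be noted at clinic.

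**After the fix.** With one question, one schedule and one recall period in both arms, detection is the same in each, and equal true rates give an expected ratio of 1.00.

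**The case against.** The strongest reply is that usual care is not unobserved. Clinic visits are frequent in the first six months, social-work and mental-health visits are tracked in both groups, participants have device support by phone, and anyone may withdraw and be asked why. Adverse-event reports are split by treatment phase, so the nine-week period can be viewed separately. Appendix X may already set a common procedure. This stands to the extent that it makes the size of the distortion uncertain and could make it small. It does not remove the asymmetry. The chart extraction listed in Section 9.5 does not include non-serious adverse events, visit tracking in Section 9.3 is intended for covariates, and the discomfort and upset named in Section 13.0 need not be charted. Splitting by phase shows where the asymmetry lies without correcting it.

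Three stronger readings are tempting, and the documents support none of them.

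- *A false safety signal is likely.* No safety test, endpoint or stopping rule rests on these tables, and Section 13.0 reports very few non-serious events in the team's earlier supportive-care studies. A false-positive rate for a test that nobody plans, at an assumed high event rate, does not measure harm here.
- *Usual-care dropout cannot appear before about Week 8.* Section 12.0 allows withdrawal at any time, and Section 11.0 has coordinators record disease-related attrition. The effect is a lag. A PATH excess that remains after the window could also be real, because only PATH has sessions to refuse.
- *The ethics-board summary is distorted to the same degree.* It covers study-related events only. Discomfort caused by the calls can arise only in PATH, so some excess there would be genuine.

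**Conclusion.** The point holds as a tendency of unknown size. In Weeks 0-9, equal true rates of non-serious events will tend to look higher in PATH unless recall or chart capture is complete. The illustrative range is a ratio of about 1.1 to 2.8; it is lower if events are also charted or if the Week-8 contact brings them out, and 1.0 under full capture. These figures rest on an assumed recall model, since the documents give no detection rate. Over Weeks 0-18 the same assumptions give 1.05 to 1.88.

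The dropout part is confined to timing: PATH losses are known earlier, and cumulative counts equalise once the Week-9 window closes.

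No primary result or planned test changes. The correction is still worth making, because the protocol commits to reporting these rates by arm and the cost is small. If Appendix X already sets a common question and recall period, the adverse-event part falls away and Section 11.0 need only cite it.

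**What to change.** 1. If Appendix X defines a common adverse-event procedure, cite it in Section 11.0. Otherwise add the same brief adverse-event question, with the same recall period, to the Week-9 and Week-18 surveys in both arms, and list it in Table 4.
2. Record how each event was found: common survey, health record, PATH call or spontaneous report.
3. Base the between-arm rate on the common sources, with participants assessed at that point as the denominator for survey-found events. An event mentioned on a call and also reported in the survey counts. List events found only on PATH calls separately, for PATH.
4. Say in Section 11.0 that between-arm dropout is interpreted at Weeks 9 and 18, and that weekly counts before then reflect earlier knowledge in PATH.
5. Keep the monthly and weekly monitoring reports and the review of individual events as planned.

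The cost is some wording, one source field and one survey item at two existing assessments. The downside is that the like-for-like comparison is available only at the assessment points.

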12.0 Withdrawal of Subjects*

We do not anticipate any circumstances under which the subjects will be withdrawn from the research without their consent. We do not anticipate any termination of participants. When informed consent is being obtained from patients, we will emphasize to patients that they can withdraw from the study at any time for any discomforts. Participants who withdraw from the study will still have their data potentially analyzed depending on when in the study they withdraw, and participants will be informed of this as well. We will ensure that contact with participants is confidential by using only the phone numbers and other contact information that are specifically allowed by the participants and not leaving study-related messages for participants unless expressly

PROTOCOL TITLE: Randomized Trial of a Positive Psychology Intervention for Patients with Hematologic Malignancies Undergoing Hematopoietic Stem Cell Transplantation

allowed by participants. Upon enrollment, we ask all participants if it is acceptable to leave voice messages on their phones, as well as the appropriate times to call them. We adhere to any and all participant requests regarding contact. If a participant requests withdrawal from the study, we will ask them if they are comfortable sharing the reason for withdrawal to ensure that there are no adverse events to report to the IRB. We will ask the study participant if they are still willing to permit the study team to continue to monitor their health record, but withdraw from all other study procedures.

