Digital recordings of the sessions and exit interviews will be completed using portable recorders. If a study participant were to refuse audio recordings, they can either remove themselves from the study or work with the study staff to choose an alternative to audio recording such as transcription. All recordings will be downloaded immediately from the recorders and the electronic files will be kept within the firewalled, password-protected file on a Partners/Mass General Brigham/DFCI server. Recordings will contain minimal personally identifiable information as the recordings will include the participant's voice but their names or other identifying information on the recordings will not be used and will be erased following review.

All data regarding the objective adherence devices will be encoded only with the study participant number that is linked to personal identifying information in the study database. The devices will not be marked with any personal identifiable information, and the database that will be used to monitor medication adherence and accelerometer data will only contain participant numbers. Data that is uploaded from each participant's accelerometer will be coded without identifying information and will be accessed from a locked computer in a research team office.

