We will compare between-group differences in change over time in all patient-reported outcome measures (i.e., psychological, functional, and QOL outcomes) at the 9 and 18-week time points using random effects regression models with a random intercept for each patient. Longitudinal analyses will include all time points. The model will include a categorical effect of time (baseline, week 9 and week 18), a group effect and a time by group interaction. The time by group interaction will estimate the difference in the change from baseline to each time point, and these regression coefficients will be the focus of the analysis.

Given that this pilot is not powered to detect statistically significant group differences, we will examine difference in the change with time and sample variance components on the secondary outcomes. Effect sizes (Cohen's d) will be calculated for changes in outcomes from baseline to 9 and 18 weeks, where 0.3 indicates a small effect, 0.5 a medium effect, and 0.8 a large effect.⁸⁸ Effect sizes will be used in a power analysis to estimate the necessary sample size to conduct a full-scale efficacy trial with power >80%. We will also verify the needed sample size based on ability to detect a clinically meaningful difference and references to existing literature.⁸⁹

Finally, we will explore (1) possible mediators of the intervention (e.g., coping strategies) by examining the bootstrapped confidence intervals of the indirect effects and (2) possible moderators (e.g., social support) of intervention effects by probing interactions between the moderator and group assignment that reach or approach significance ($p<0.15$) when predicting patient-reported outcomes.

PROTOCOL TITLE: Randomized Trial of a Positive Psychology Intervention for Patients with Hematologic Malignancies Undergoing Hematopoietic Stem Cell Transplantation

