Specific Aim 3 (Effects on Health Behaviors): To examine the impact of the PATH intervention on behavioral outcomes (e.g., medication adherence, physical activity) compared to those in the usual care condition: We will initially compare physical activity (# of steps/day) at 9- and 18-weeks between the intervention and control groups using a Wilcoxon rank sum test, given that the distribution of the number of steps will likely be skewed. We will also use random effects regression models with a random intercept for each participant to compare between-group differences in change over time in physical activity and medication adherence. All statistical tests will be two tailed, with $p < 0.05$ considered significant.

Missing Data: We will also use the intention-to-treat principle with all randomized participants and conducting sensitivity analyses to explore various assumptions about missing data. If source of the missing data appear to be missing at random, the linear mixed effects models described above provide an unbiased estimate of the regression coefficients. However, if we find that participants do not complete the study because of disease worsening, suggesting missing data are not random, we will employ pattern mixture modeling or joint modeling approaches⁹⁰ to handle incomplete data, and perform sensitivity analysis⁹¹ to assess the impact of missing data. In addition to the intention-to-treat analysis, we will also estimate the group differences in the completers to estimate the per protocol group difference.

10.2. Sample Size Calculation & Power Analysis:

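### Section 12.0 makes use of withdrawn participants' data depend on an undefined timing rule and then offers chart review only, which does not fit the intention-to-treat analysis

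*Combined protocol and SAP*

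**What the plan says.** Section 12.0 sets the rule for data from people who leave: "Participants who withdraw from the study will still have their data potentially analyzed depending on when in the study they withdraw". It adds that participants will be told this, but defines no time point or criterion. After a withdrawal request, the only arrangement put to the participant is to "permit the study team to continue to monitor their health record, but withdraw from all other study procedures". No other form of continued participation is offered at that point.

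Section 10.1 (Missing Data) says: "We will also use the intention-to-treat principle with all randomized participants". The longitudinal model in the same section covers baseline, week 9 and week 18: "Longitudinal analyses will include all time points". A completer analysis is planned in addition. Pattern-mixture or joint modelling is to be used "if we find that participants do not complete the study because of disease worsening, suggesting missing data are not random". Withdrawal by choice is not named as a trigger, although sensitivity analyses under various missing-data assumptions are promised in general terms.

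Section 5.1 counts participants who withdraw towards accrual and does not replace them. Section 11.0, on attrition, treats people who decline further intervention sessions after enrolling as one source of loss.

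**The concern.** Two parts of Section 12.0 pull against the analysis plan.

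- **Data already collected.** Whether they are used is left open and tied to timing, with no rule. Section 11.0 gives the team weekly retention and dropout reports by treatment group, so an unwritten cut-off could be settled by people who know the arm.
- **Data not yet collected.** Someone who wants to leave is taken straight to chart review. The record items in Section 9.5 are clinical and transplant characteristics, GVHD and relapse. Quality of life, mood, optimism, affect, activity and adherence cannot be recovered from them.

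At stake are the between-arm estimates for the secondary outcomes. Section 10.1 carries their effect sizes into the sample-size calculation for the next trial. If leavers differ from stayers, and leave at different rates or for different reasons by arm, those effect sizes are biased. The primary aim is feasibility and acceptability, so this concerns the secondary aims.

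**Working it through.** **1. The plan's own figures.** Section 10.2 enrols 35 per arm, allows 15% loss from medical complications and death, and plans on 30 completing in each arm: 35 × 0.85 = 29.75, about 30. With 30 per arm, a two-sample t-test (two-sided alpha 0.05, 80% power) detects d = 0.736. The stated 0.74 reproduces.

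**2. Is precision the problem?** Hardly. Holding 60 completers in total and varying the split between PATH and usual care (the splits are assumptions):

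| PATH / usual care | Detectable d, 80% power |
|---|---|
| 30 / 30 | 0.736 |
| 28 / 32 | 0.737 |
| 26 / 34 | 0.742 |
| 25 / 35 | 0.746 |

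If all 35 per arm gave outcomes, d would be 0.68. That is an upper bound, because deaths cannot be recovered by any withdrawal rule. The issue is bias and an undefined rule.

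**3. Where the gap arises.** Setting the sections side by side:

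- Section 13.0 lets sessions be put off or stopped at a participant's request and does not call this withdrawal.
- Sections 9.1, 9.6 and 9.7 schedule follow-up assessments for all participants in both arms, without conditioning on sessions completed.
- Section 12.0 applies only once a participant asks to leave the study.

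Someone who merely stops taking calls should therefore still be surveyed. The loss occurs when a participant asks to withdraw and is not offered the option of stopping the calls while continuing the assessments.

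**4. What the model can use.** Under the sequence in Section 5.1, baseline assessments precede registration and registration precedes randomisation. Every randomised participant should then have baseline data, and anyone leaving after week 9 may have more. The mixed model can use all of it, provided Section 12.0 does not allow it to be set aside.

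**5. Illustrative size of bias.** Let f be the fraction of an arm lost, and D the amount (in SD) by which the lost participants' mean is worse than the retained mean m. The full-arm mean is (1 − f)m + f(m − D) = m − fD, so the completer mean is too favourable by f × D. The documents give neither f nor D. Taking 5–15% for f and 0.3–1.0 SD for D as assumptions, with no loss in usual care:

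| f | D = 0.3 | D = 1.0 |
|---|---|---|
| 0.05 | 0.015 SD | 0.05 SD |
| 0.15 | 0.045 SD | 0.15 SD |

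Against the d = 0.3 that Section 10.1 calls small, 0.015 / 0.3 = 5% and 0.15 / 0.3 = 50%.

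The bias in the group difference is f × D in PATH minus f × D in usual care. With equal loss and equal D it is zero. These are completer-mean figures; the mixed model recovers part of the bias through the data it retains.

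**The case against.** The strongest case on the other side has five parts.

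- **The sentence is inclusive in tone.** It can be read as saying that whatever was collected before leaving will be used, which the mixed model handles. This stands in part: it is an undefined rule, not an explicit exclusion. It is still conditional, and participants are to be told so.
- **Stopping calls is not leaving.** A reader might infer that every PATH participant who gives up the calls loses all later outcomes. Sections 9.1, 9.6, 9.7 and 13.0 do not support that.
- **Nothing shows that loss falls mainly on PATH.** A reader might infer this from the burden of weekly calls. Section 12.0 covers both arms, Section 10.2 plans equal completion, and Section 11.0 reports that in the earlier trial everyone who started completed all sessions. What remains is a risk: Section 11.0 counts refusal of later sessions as attrition, and only PATH has sessions.
- **The 15% is not a withdrawal rate.** It is attributed to medical complications and death, so it cannot be turned into a count of voluntary leavers that new wording would rescue.
- **Safeguards exist.** Section 10.1 promises general sensitivity analyses, Section 11.0 requires refusal records and reports by arm, and Section 10.1 also checks the next sample size against a clinically meaningful difference. These help, but none defines which data are kept or retrieves outcomes never requested.

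Section 9.8 might also seem to push out PATH participants who refuse recording. It already offers an alternative, so no change is needed there. The consent form is not among the documents and may contain further options.

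**Conclusion.** The point holds as a mismatch to be reconciled. Section 12.0 attaches an undefined timing condition to data that the intention-to-treat analysis in Section 10.1 needs, and its only stated offer on withdrawal gives up week-9 and week-18 outcomes that some participants might still provide. The named trigger for missing-not-at-random modelling does not cover voluntary withdrawal.

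The size of any bias cannot be derived from the documents. The 0.015–0.15 SD range rests on assumed loss of 5–15% confined to PATH, assumed differences of 0.3–1.0 SD, and a completer mean. It shrinks under the mixed model and is near zero if loss is similar in both arms. Greater loss in PATH is plausible but undocumented. The affected outcomes are secondary, in a pilot that Section 10.2 says is not designed to detect group differences definitively. The change is worth making because it costs so little.

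**What to change.** 1. **Section 12.0, data already collected.** State that all data collected up to withdrawal of consent are kept and analysed in the randomised arm, unless the participant revokes permission. Delete the timing condition.
2. **Section 12.0, data still to come.** When a participant asks to withdraw, offer in order: stop the exercises and calls but complete the week-9 and week-18 assessments; surveys only; chart review only; full withdrawal. Record which was chosen.
3. **Section 10.1, Missing Data.** Extend the missing-not-at-random sensitivity analysis from disease worsening to withdrawal for any reason, and report withdrawals and reasons by arm.

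The cost is protocol wording, matching consent text, and a few extra survey contacts with participants who have stopped the calls.
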